3.2 Secondary Objectives

- **3.2.1** To further describe the adverse events associated with using PSMA-PET/MRI to define radiotherapy target volumes in subjects with unfavorable-risk prostate cancer.
- **3.2.2** To evaluate biochemical control after radiotherapy in subjects who have received PSMA-PET/MRI to define radiotherapy target volumes.
- 3.2.3 To measure patient-reported quality of life prior to radiation therapy and over time in subjects with prostate cancer who have received PSMA-PET/MRI to define radiotherapy target volumes.
- **3.2.4** To determine the proportion of screened subjects who are enrolled on the study.

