3.3 Exploratory Objectives

4.0 STUDY ENDPOINTS

4.1 Primary

The planning criteria that will be used are the current standard of care and standard practice at UNC and includes defined treatment volumes with a prescribed dose while respecting the dose constraints to all organs at risk. The primary endpoint is grade 3+ late genitourinary toxicity and gastrointestinal toxicity as classified and graded according to the National Cancer Institute's Common Terminology Criteria for Adverse Events (CTCAE), version 5.0 at 12 months after radiation therapy.

- 4.2 Secondary
- 4.2.1 Grade 3+ acute and late genitourinary and gastrointestinal toxicity will be defined according to CTCAE, version 5.0 during radiation therapy and at 1, 3, 6, 9, 12, 18, 24, 30, 36, 42, 48, 54 and 60 months post radiotherapy. Additionally, this will be reported as a cumulative incidence over the entire 5-year course of the study.
- 4.2.2 Biochemical control will be defined according to the Phoenix criteria³³ (PSA rise of 2 ng/mL over nadir) at 2 and 5 years after radiation therapy.
- 4.2.3 Patient reported quality of life will be measured using the Expanded Prostate Cancer Index Composite (EPIC-26) and the Urinary Obstruction/Irritation scale of the validated Prostate Cancer Symptom Indices (PCSI). Patient reported quality of life will be measured before the start of radiation therapy at 1, 3, 6, 9, 12, 18, 24, 30, 36, 42, 48, 54, and 60 months post radiotherapy.
- 4.2.4 The total number of subjects enrolled on the study will be compared to the total number of screened subjects.
- 4.2.5 The feasibility of meeting dose constraints will be defined as the proportion of subjects who meet the following dose constraint criteria:
 - SBRT-CK boost dose prescription: 6.5Gy x 3
 - PTV: V19.5Gy > 95%
 - PTVmax > 150%, CI < 1.8
 - CTV: V19.5Gy > 99%
 - \circ DIL: V24.0Gy > 99%

- SBRT-CK boost dose constraints:
 - o Rectum
 - V21.1Gy< 5 %
 - V18.9Gy< 20 %
 - V17.5Gy<10 %
 - V16.2Gy< 40 %
 - V10.2Gy< 60 %
 - V9.3Gy< 40 %
 - V19.5Gy<1cc
 - Max<21.2Gy
 - Bladder
 - V21.1Gy< 5 %
 - V19.5y < 5 cc
 - V9.3Gy<40 %
 - Max<21.2Gy
 - Prostatic Urethra
 - V19.5Gy > 95%
 - V22Gy < 0.03cc
 - Membranous Urethra
 - V18 Gy < 50%
 - Large bowel
 - V15Gy<1cc
 - Small bowel
 - V15Gy<1cc
 - Penile bulb
 - V15Gy< 3cc

4.2.6 Performance of PSMA-PET/MRI to PSMA PET/CT as defined as:

- Rate of identification and delineation of DIL (e.g. sensitivity and specificity)

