10.0 STATISTICAL CONSIDERATIONS

10.1 Study Design/Study Endpoints

This will be a prospective, single-arm, non-randomized, phase II study to examine the feasibility and acute and late toxicities of standard radiation treatment for unfavorable intermediate and high risk prostate cancer - this involves a combination of external beam radiation therapy and SBRT-CK and androgen deprivation therapy – while using advanced imaging modalities (PSMA/PET-mpMRI) to intelligently adapt the radiation fields. The radiation therapy usually takes 2 months and the follow up is 60 months, while the duration of the evaluation of the final results will be about 12 months after the end of treatment.

There is one primary endpoint:

(1) Late genitourinary toxicity and gastrointestinal toxicity at 12 months (these will be recorded at 1, 3, 6, 9, 12, 24, 36, 48 and 60 months after radiotherapy, according to CTCAE v5).

Table 1 shows an overview of late toxicities in randomized studies of conventionally fractionated schemes in primary prostate carcinoma. On average, the rate of late GI / GU toxicities of grade 2 or higher averaged a rate of approximately 16%.

Study	1 ³⁸	2 ³⁹	3 ⁴⁰	4^{41}	5 ⁴²	6 ⁴³				
Patient #	296	151	101	478	372	1065				
Total dose (Gy)	76	76	75.6	86.4	76	74				
Fractions #	38	38	42	39	38	37				
Dose/fraction (Gy)	2	2	1.8	2	2	2				
Late Reactions – RTOG G2+										
GI (%)	9	22.5	5.1	3.7	8	13.7				
GU (%)	19	13.4	16.5	15.5	24	9.2				

 Table 1 Summary of results from recent clinical trials with external beam radiotherapy.

Table 2 shows an overview of late toxicities in randomized studies of combination external beam radiotherapy and SBRT in primary prostate carcinoma. On average, the rate of late Grade 2 or higher GU toxicities is $\sim 11.4\%$ and for GI toxicities $\sim 6\%$.

Table 2 Summary of results from randomized	clinical	trials	treating	with	combination
external beam radiation therapy and SBRT.					

Study	1 ⁴⁴	2 ⁴⁵	3 ⁴⁶	4 ⁴⁷	5 ⁴⁸	6 ⁴⁹	7 ⁵⁰	8 ⁵¹
Patient #	121	26	76	39	108	48	41	45
EBRT dose (Gy)	45	44	46	45	45-50.4	45	45	45
EBRT Fractions #	25	20	23	25	25-28	25	25	25
CK dose (Gy)	21	18 or 21	18	21	19.5	19 or 21	21	18-21
CK Fractions #	3	3	3	3	3	2	3	3
		Late T	'oxicity –	Grade 2	+			
GI (%)	3.4	4.0	9.3	12.8	5.0	0.0	0.0	13.3
GU (%)	20.6	4.0	1.4	10.3	13.7	27.0	11.0	2.9

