10063057	Renal and urinary disorders	Cystitis noninfective	Microscopic hematuria; minimal increase in frequency, urgency, dysuria, or nocturia; new onset of incontinence	Moderate hematuria; moderate increase in frequency, urgency, dysuria, nocturia or incontinence; urinary catheter placement or bladder irrigation indicated; limiting instrumental ADL	Gross hematuria; transfusion, IV medications, or hospitalization indicated; elective invasive intervention indicated	Life-threatening consequences; urgent invasive intervention indicated	Death
10013990	Renal and urinary disorders	Dysuria	Present	-	-	-	-
10068405	Renal and urinary disorders	Glucosuria	Present	-	- Gross hematuria; transfusion, IV medications,	- Life-threatening consequences;	-
10019450	Renal and urinary disorders	Hematuria	Asymptomatic; clinical or diagnostic observations only; intervention not indicated	Symptomatic; urinary catheter or bladder irrigation indicated; limiting instrumental ADL	or hospitalization indicated; lective invasive intervention indicated; limiting self care ADL	urgent invasive intervention indicated Life-threatening consequences;	Death
10065368	Renal and urinary disorders	Urinary fistula	-	Symptomatic, invasive intervention not indicated Limiting instrumental ADL; medical management	Invasive intervention indicated	urgent invasive intervention indicated	Death
10046539	Renal and urinary disorders	Urinary frequency Urinary incontinence	Present Occasional (e.g., with coughing, sneezing,	indicated Spontaneous; pads indicated; limiting	- Intervention indicated (e.g., clamp, collagen injections); operative intervention indicated;	-	-
10040543	nenal and urinary disorders	or intary incontinence	etc.), pads not indicated Urinary, suprapubic or intermittent catheter	instrumental ADL Placement of urinary, suprapubic or intermittent	injections); operative intervention indicated; limiting self care ADL Elective invasive intervention indicated;	- Life-threatening consequences;	-
10046555	Renal and urinary disorders	Urinary retention	placement not indicated; able to void with some residual	catheter placement indicated; medication indicated	substantial loss of affected kidney function or mass	organ failure; urgent operative intervention indicated	Death

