10061574	Renal and urinary disorders	Urinary tract obstruction	Asymptomatic; clinical or diagnostic observations only; intervention not indicated	Symptomatic but no hydronephrosis, sepsis, or renal dysfunction; urethral dilation, urinary or suprapubic catheter indicated	Altered organ function (e.g., hydronephrosis or renal dysfunction); invasive intervention indicated	Life-threatening consequences; urgent intervention indicated	Death
	Renal and urinary disorders	Urinary tract pain	Mild pain	Moderate pain; limiting instrumental ADL Limiting instrumental ADL; medical management	Severe pain; limiting self care ADL	-	-
10046593	Renal and urinary disorders	Urinary urgency	Present	Limiting instrumental ADL; medical management indicated	-	•	-
10046628	Renal and urinary disorders	Urine discoloration	Present	-	-	-	-

A.4 Quality of Life according to EPIC-26

The Expanded Prostate Cancer Index Composite (EPIC-26) scoring protocol was designed to measure Quality of Life issues in patients with Prostate cancer.

1. Ove	er the past 4 weeks, how often hav	ve you le	eaked urine?			
	More than once a day		1			
	About once a day		2			
	More than once a week		3 (Circle	e one numbe	er)	
	About once a week		4			
	Rarely or never		5			
2. Which	ch of the following best describes y	our urin	ary control du	ring the las	t 4 weeks?	
	No urinary control whatsoeve	•r		1		
	Frequent dribbling			2	(Circle one nu	umber)
	Occasional dribbling			3		
	Total control			4		
	/ many pads or adult diapers per da ring the last 4 weeks?	ay did y	ou usually use	to control le	eakage	
	None			0		
	1 pad per day			1		
	2 pads per day			2	(Circle one nu	umber)
	3 or more pads per day			3		
4. How	big a problem, if any, has each of	the follo	wing been for	you during	the last 4 wee	ks?
	(Circle one number on each line)					
	Annual and the second sec	No roblem	Very Small Problem	Small Problem	Moderate Problem	Big Problem
a.	11 5 5	0	1	2	3	4
b.	3	0	1	2	3	4
с.	9	0	1	2	3	4
d.	Weak urine stream				-	
	or incomplete emptying		1	2	3	4
e.	Need to urinate frequently during	1				

5. Overall, how big a problem has your urinary function been for you during the last 4 weeks?

1

No problem1
Very small problem2
Small problem3
Moderate problem 4
Big problem5

the day..... 0

(Circle one number)

3

4

2

LCCC 1908 PI: [name]

CONFIDENTIAL UNIVERSITY OF NORTH CAROLINA July 24, 2024

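### Endpoint 4.2.1 reports toxicity only at grade 3+, a level that urinary frequency, urgency and dysuria cannot reach under their own terms in Appendix A.3; adding grade 2+ would fix most of this at little cost

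*Combined protocol and SAP*

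**What the plan says.** Secondary objective 3.2.1 is broad: "To further describe the adverse events associated with using PSMA-PET/MRI to define radiotherapy target volumes". Endpoint 4.2.1 puts it into practice with a grade floor: "Grade 3+ acute and late genitourinary and gastrointestinal toxicity will be defined according to CTCAE, version 5.0 during radiation therapy", and then at 1 to 60 months after radiotherapy. Section 4.2.1 continues: "Additionally, this will be reported as a cumulative incidence over the entire 5-year course of the study". The synopsis repeats the grade 3+ wording without the cumulative-incidence sentence.

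Appendix A.3 sets out the CTCAE v5 terms and grades. Dysuria has a single entry, at grade 1 ("Dysuria Present"). The highest entry for urinary urgency is grade 2: "Limiting instrumental ADL; medical management indicated". Urinary frequency likewise has entries at grades 1 and 2 only.

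Section 10.1 gives historical rates for late toxicity, all at grade 2 or higher. For combined external beam and SBRT treatment it says "the rate of late Grade 2 or higher GU toxicities is" about 11.4%, with about 6% for GI. Section 10.3 promises acute and late toxicity rates with 95% confidence intervals but does not say at which grade.

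**The concern.** An endpoint meant to describe adverse events has a threshold above the top of the scale for three irritative urinary symptoms. A zero for these terms in 4.2.1 would follow from the definition and would say nothing about the treatment.

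The plan gives a reason to look at urinary symptoms. Section 6.1.1.3 prescribes 24.0 Gy to PTV5 inside a boost of 19.5 Gy to PTV4, subject first to the urethra, bladder and rectum constraints. Section 2.2 frames the safety question as whether side effects increase relative to historical data. A grade 3+ cumulative incidence cannot be set directly against grade 2+ historical rates. A reader of the final report could also take a low grade 3+ figure as covering symptoms that it cannot contain.

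**Working it through.** 4.2.1 is descriptive and has no sample size, power or alpha to reproduce. The check compares its threshold with the scale and then with the other places where toxicity is reported.

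**1. Threshold against scale.** The threshold is grade 3 (4.2.1).

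| Term in A.3 | Highest grade available | Can reach grade 3? |
|---|---|---|
| Dysuria | 1 | No |
| Urinary frequency | 2 | No |
| Urinary urgency | 2 | No |

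In the text version of A.3 the frequency row runs into the next one ("Urinary frequency Urinary incontinence"). The grade 3 wording found there, "Intervention indicated (e.g., clamp, collagen injections); operative intervention indicated", belongs to incontinence. It is preceded by a dash, which is the empty grade 3 cell for frequency. Every GI term listed in A.3 has a grade 3 entry, so the ceiling is a GU matter only.

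**2. Other routes to grade 3.** Noninfective cystitis names frequency, urgency and dysuria at grade 2. Its grade 3 requires gross hematuria, transfusion, IV medication, hospitalization or elective invasive intervention. Severe painful urination might instead be coded as urinary tract pain, whose grade 3 is severe pain limiting self-care. A severe case can therefore count, but only by meeting another term's criteria.

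**3. Grade of the benchmarks.** The second table in 10.1 gives late grade 2+ rates for eight studies. Their unweighted means reproduce the plan's figures:

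- GU: (20.6 + 4.0 + 1.4 + 10.3 + 13.7 + 27.0 + 11.0 + 2.9) / 8 = 90.9 / 8 = 11.4%
- GI: (3.4 + 4.0 + 9.3 + 12.8 + 5.0 + 0.0 + 0.0 + 13.3) / 8 = 47.8 / 8 = 6.0%

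The first table is also late grade 2+ (RTOG). Neither table gives an acute rate.

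**4. Where grade 2 toxicity is reported.**

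| Period | Place in the plan | Grade |
|---|---|---|
| Acute | 4.2.1 | 3+ |
| Acute | Dose-limiting toxicity, 6.4 and 7.1.4 | 3+ |
| Acute and late | Rates in 10.3 | Not stated |
| Late, at 12 months | Test in 10.1 | 2+ |
| Late, 18 to 60 months and cumulative | 4.2.1 | 3+ |

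No endpoint explicitly reports acute grade 2 toxicity, or late grade 2 toxicity beyond 12 months.

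**5. What is recorded.** Section 7.1.4 has severity or grade entered on the case report form with no floor, and 9.2 requires documentation of non-serious events with their grade through five years. The data for a grade 2+ summary should therefore exist.

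**The case against.** The strongest reply is that the symptoms are already measured elsewhere. Endpoint 4.2.3 uses EPIC-26 and the PCSI Urinary Obstruction/Irritation scale before radiotherapy and at every post-treatment visit listed in 4.2.1. EPIC-26 asks about daytime frequency, and the PCSI sheet asks about night-time urination, frequency, pain or burning, and urgency. A lasting rise should appear there. This stands and limits the harm, but does not remove it. The Time and Events Table schedules no quality-of-life assessment during radiation. Section 10.3 summarises the scores by mean, standard deviation, median and range, which gives no rate to set beside the benchmarks in 10.1.

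Second, grade 3+ is a legitimate severity threshold, and 10.3 could be read as covering all grades. That is possible, but 10.3 names no grade and the only stated grade for acute GU/GI toxicity is 3+. The plan should say which is meant.

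Third, the late part might seem to be the conflict between grade 3+ in 4.1 and grade 2+ in 10.1. Settling that conflict would fix the 12-month analysis but leave the acute and later follow-up reporting in 4.2.1 unchanged.

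Three stronger readings are tempting, and the documents do not support them.

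- A reader might count 5 of the 14 renal and urinary terms in A.3 as having no grade 3 and call 36% of GU toxicity invisible. Two of the five are glucosuria and urine discoloration, which carry little weight here, and a share of terms is not a share of events.
- A reader might suppose that all late grade 2+ GU events are frequency or urgency, so that 4.2.1 would show 0 of 38. Nothing in the documents supports that split. Any set of purely grade 2 events would give the same zero, including terms with a full scale, so the figure reflects the threshold and not the ceiling.
- A reader might infer that an acute historical comparison is being lost. The plan contains no acute historical rates.

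**Conclusion.** The point holds as a reporting gap of limited size. Dysuria, urinary frequency and urinary urgency contribute exactly zero to 4.2.1 under their own terms, and the late and cumulative figures in 4.2.1 are one grade stricter than the benchmarks in 10.1. The share of GU events missed cannot be estimated, because the documents give no breakdown of events by term. It could be anything from negligible to most of the grade 2 events.

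No data are lost and the test in 10.1 is not affected. The conclusion assumes that events are coded under the terms in A.3 and that 4.2.1 is applied as written. Reporting grade 2+ would make the late figures comparable in grade with 10.1. Scale and follow-up time could still differ: the first table uses RTOG grading, and neither table states a time horizon.

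Early closure does not make the point moot, since 10.3 applies the same analysis plan to the data available at termination.

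**What to change.** Amend 4.2.1 and the matching synopsis entry to report acute and late GU and GI toxicity at both grade 2+ and grade 3+, by visit and as cumulative incidence, each with a 95% confidence interval. Carry the cumulative-incidence sentence into the synopsis as well.

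Add a listing of urinary frequency, urgency and dysuria by maximum grade. The listing is needed because a grade 2+ summary would still miss dysuria under its own term.

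State in 10.3 that its acute and late toxicity rates use these grades. If the protocol is not amended again before the final analysis, present the grade 2+ tables in the report and label them as added.

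The cost is a little more tabulation. No new data collection, visits or patients are needed, because all grades are already recorded under 7.1.4 and 9.2.

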5.0 PATIENT ELIGIBILITY

5.1 Inclusion Criteria

Each subject must meet all of the following inclusion criteria to participate in this study.

- 5.1.1 Written informed consent obtained to participate in the study and HIPAA authorization for release of personal health information.
- 5.1.2 Male subjects \geq 18 years of age
- 5.1.3 Histologically confirmed prostate adenocarcinoma
- 5.1.4 Unfavorable intermediate or high-risk, based on the NCCN criteria³¹ (Appendix A.1), with appropriate staging (e.g. bone scan).
- 5.1.5 Subject has adequate performance status as defined by ECOG performance status of 0-2. (Appendix A.2)
- 5.1.6 Subject is willing and able to comply with the protocol as determined by the Treating Investigator.
- 5.1.7 Subject speaks English (quality of life instrument is validated in English)

5.2 Exclusion Criteria

All subjects meeting any of the following exclusion criteria at baseline will be excluded from study participation.

5.2.1 Contraindications for MRI

[figure not shown]
5.2.2 Other prior or concomitant malignancies with the exception of:

- Non-melanoma skin cancer
- Other cancer for which the subject has been disease free for ≥5 years before the first study treatment and of low potential risk for recurrence.

5.2.3 Inflammatory bowel disease

6.0 TREATMENT PLAN

6.1 Treatment Overview

6.1.1 Subsection for Radiation Delivery Details

6.1.1.1 Preparation process for radiotherapy

6.1.1.1.1 PET CT and MRI

- The subject will start ADT on the day of or after PSMA-PET/MRI. ADT can be administered at UNC or at Subject's local providers. Prior to radiation planning, the subject will have three MRI-compatible fiducials placed into the prostate by an urologist or radiation oncologist. These will be used for image registration purposes.
- 1-2 weeks after fiducial placement, the subject will undergo PSMA-PET/MRI (pelvis) scan at the BRIC. The subject will be injected with ~0.07 mCi/kg body weight ⁶⁸Ga-PSMA-11. Subject will undergo a PET/MR of the pelvis

CONFIDENTIAL UNIVERSITY OF NORTH CAROLINA July 24, 2024

with simultaneous acquisition of multi-parametric (mp)MR sequences and PET about 60 minutes after radiotracer injection (Siemens Biograph mMR). During the uptake period of 60 minutes, the subject should drink at least 500 mL of fluid (water or fluid of choice). The subject should void immediately prior to PET/MR acquisition. The MR sequences to be acquired are shown in Sequences of the mpMRI protocol). PET/MR acquisition takes A.6 about 30 minutes. Intravenous contrast will be administered for the mpMRI. All PET images will be reconstructed with corrections for attenuation, dead time, random events, and scatter, using iterative ordered-subsets expectation maximization. PET images in PET/MR will be acquired in list mode and reconstructed for several time points after scan start time and durations adjusted for radioisotope decay: e.g. 0-5 min, 5-10 min, 15-21 min and 21-28 min. No Lasix will be used for the PSMA-PET/MRI imaging acquisition. For the first five protocol subjects, if real-time reconstruction does not produce satisfactory images, the option to have the subject void (i.e. urinate) and reimage will be considered.

- a. 68Ga-PSMA PET scans co-registered with MRI scan with IV contrast. 68Ga-PSMA PET scans will be performed with co-registration with MR with contrast before starting radiation therapy. A commercial PSMA kit will be used to source the 68Ga-PSMA radiotracer and will be infused into the subject at the BRIC facility. These images with be acquired on the PET/MR scanner available at the Biomedical Research Imaging Center (BRIC). PET/MR will of the pelvis. Subjects will remain in a quiet room for 60 minutes after injection of the 68Ga-PSMA to allow for uptake of the tracer and excretion of non-localized radioactivity. Subjects will then undergo a PET/MR scan of the pelvis including multiparametric MR. Participants must have their 68Ga-PSMA PET scan performed at UNC-CH.
- b. Administration, scanning and analysis of [68Ga]-PSMA. Initially, a venous line will be established for the administration of ⁶⁸Ga-PSMA, irrespective of whether the patient already has a central line (e.g. Mediport, Port-a-cath, PICC line). In other words, these central lines will NOT be used for infusion of the radionuclide agent. Intravenous administration of ⁶⁸GA-PSMA [0.07 mCi/kg \pm 10%] will be administered under the supervision of [name] or another qualified nuclear medicine physician from the Nuclear Medicine Department. 68Ga-PSMA PET/MR imaging will commence 60 minutes following injection.
- 3. Per UNC standard practice patients with high-risk disease will undergo elective pelvic nodal irradiation. Patients with unfavorable-intermediate risk disease will receive elective nodal irradiation at the discretion of the treating physician (e.g. secondary to suspicious imaging findings or high nomogram predicted incidence of occult nodal disease). If the PSMA imaging alone shows suspicious pelvic nodes, a biopsy of the suspicious node will be offered, and upon confirmation, these may be included in the external beam radiation treatment field.

4. Because the PSMA-PET/MRI may find distant disease that may otherwise not have been found, if the use of the PSMA-PET or MRI information suggests that the patient has M1 disease, the patient will be re-referred to the UNC multidisciplinary Urologic Oncology clinic for consultation to discuss 1) the implication of these findings, 2) what additional systemic agents should be used in their treatment regimen, if any, and 3) how these findings may impact the utility of this study. This would not exclude them from the study.

